#### **7.5.1.2 Adverse Drug Reactions**

All noxious and unintended responses to an investigational medicinal product (IMP; i.e., where a causal relationship between an IMP and an AE is at least a reasonable possibility) related to any dose should be considered adverse drug reactions.

#### **7.5.1.3 Adverse Event of Special Interest**

An adverse event of special interest (AESI) is an adverse event (serious or nonserious) of scientific and medical concern, specific to the IMP or program, for which ongoing monitoring and rapid communication by the Investigator to the Sponsor may be appropriate. Such events may require further investigation on site in a timely manner by the investigator or designee in order to characterize and understand them. AESIs may be added or removed during a study by protocol amendment. Angioedema is considered as an AESI for detailed reporting and timely processing.

#### **7.5.1.4 Serious Adverse Events**

An SAE is defined as any untoward medical occurrence that at any dose:

- results in death, includes all deaths, even those that appear to be completely unrelated to study drug (e.g., car accident where subject is a passenger)
- is life-threatening. An AE is life-threatening if the subject was at immediate risk of death from the event as it occurred (i.e., does not include a reaction that might have caused death if it had occurred in a more serious form). For instance, drug-induced hepatitis that resolved without evidence of hepatic failure would not be considered life-threatening even though drug-induced hepatitis can be fatal.
- requires inpatient hospitalization or prolongation of existing hospitalization. Hospitalization signifies that the subject has been admitted to the hospital or short-stay-type unit, or an emergency room stay for longer than 24 hours for observation and/or treatment at a level of care which would not have been appropriate at the study site. Hospitalization for elective treatment of a pre-existing non-worsening condition or, which is not the result of an AE, are not considered an AE. The details of such hospitalizations must be recorded on the medical history or physical examination page of the eCRF. Complications occurring during hospitalization are AEs and are SAEs if they cause prolongation of the current hospitalization or meet other criteria that define SAEs.
- results in persistent or significant disability/incapacity. Disability is defined as a substantial disruption of a person's ability to conduct normal life functions. An AE is incapacitating or disabling if it results in a substantial and/or permanent disruption of the subject's ability to carry out normal life functions.
- is a congenital anomaly/birth defect
- is an important medical event

- Any suspected transmission via a medicinal product of an infectious agent reaction.

[figure not shown]
Important medical events that may not result in death, be life-threatening, or require hospitalization may be considered SAEs when, based upon appropriate medical judgment, they may jeopardize the subject and may require medical or surgical intervention to prevent one of the outcomes listed in this definition.

All SAEs will be followed until resolution, until the Investigator and the Sponsor agree that follow-up is no longer necessary, or the subject withdraws consent or is lost to follow-up.

#### Serious Adverse Event and AESI Reporting

##### Investigator Reporting Responsibilities to the Sponsor

SAEs and/or AESI due to any cause, whether or not related to the study drug, must be reported to the Sponsor or designee within 24 hours of occurrence or when the Investigator becomes aware of the event. A completed SAE report form must be submitted including a full description of the event and sequelae in the format detailed in the SAE reporting form. The following contact information is to be used for SAE reporting:

The event must also be recorded on the standard AE eCRF. Preliminary reports of SAEs must be followed by detailed descriptions as soon as possible including clear and redacted photocopies of hospital case reports, consultant reports, autopsy reports, and other documents when requested and applicable and if available.

##### Investigator Reporting Responsibilities to IRB

Unanticipated problems posing risks to study subjects will be reported to the IRB/IEC per their institutional policy. Copies of each report and documentation of IRB/IEC notification and acknowledgement of receipt will be kept in the Investigator's study file.

##### Sponsor Reporting Responsibilities to Participating Investigators

It is the responsibility of the Sponsor or designee to immediately notify all participating Investigators of any AE associated with the use of the study drug that is both serious and unexpected, as well as any finding from tests in laboratory animals that suggest a significant risk for human subjects.

#### 7.5.2              Pregnancy

Formal reproduction toxicology testing of KPL-716 has not yet been performed.

Female subjects of childbearing potential must therefore agree to use a highly effective and protocol approved contraceptive method ([Section 6.5](#)) for the duration of the study and until

16 weeks after last study drug administration under this protocol. Regular pregnancy tests will be performed for female subjects of childbearing potential, as defined in [Appendix 1](#).

Male subjects who have a female partner of childbearing potential must agree to use a highly effective and protocol approved contraceptive method ([Section 6.5](#)) for the duration of the study and until 16 weeks after last study drug administration under this protocol.

If a subject becomes pregnant while participating in the study, study drug dosing must be discontinued immediately.

A female subject must immediately inform the Investigator if she becomes pregnant during the study. A male subject must inform the Investigator if his female partner becomes pregnant during the study. Pregnancies occurring up to 16 weeks after last study drug administration must be reported to the Investigator. The Investigator must report all pregnancies to the Sponsor or designee immediately and no later than 24 hours of their first knowledge of the pregnancy. The Investigator should counsel the subject that it is unknown what effects study drug might have on a fetus. Monitoring of the subject should continue until conclusion of the pregnancy.

Instances of fetal death or congenital abnormality, if brought to the attention of the Investigator at any time after cessation of the study treatment and considered by the Investigator to be possibly related to the study treatment, must be reported to the Sponsor as an SAE.

### 7.5.3 Clinical Laboratory Evaluations

Blood and urine samples will be collected for clinical laboratory evaluations (including clinical chemistry, hematology, urinalysis, and serology) at the time points specified in [Appendix 1](#).

Subjects will be asked to provide urine samples for a drugs of abuse screen at the Screening Visit and Day 1 prior to dosing and at any time during the study at the discretion of the Investigator and in consultation with the Sponsor, if needed.

For all female subjects of childbearing potential, the serum pregnancy test will be performed at the Screening Visit and the urine pregnancy test will be performed at the designated timepoints in [Appendix 1](#). Dosing should not proceed if urine pregnancy test is positive, until a negative serum pregnancy test is confirmed. Postmenopausal status will be confirmed via FSH testing at Screening.

An Investigator will perform a clinical assessment of all clinical laboratory test results.

After Screening, any clinically significant abnormal findings should be reported as AEs.

### 7.5.4 Vital Signs

Supine blood pressure (systolic and diastolic), pulse rate, respiratory rate, and body temperature will be assessed at every visit from the Screening Visit through the EOS Visit as outlined in [Appendix 1](#). Subjects must be supine for at least 5 minutes before blood pressure and pulse rate measurements.

Vital signs may also be performed at other times if judged to be clinically appropriate by the Investigator or if the ongoing review of the safety data suggests a more detailed assessment of vital signs is required. All measurements will be performed singly and may be repeated if outside the relevant clinical reference range. Additional vital sign assessments may be performed if clinically indicated, in the opinion of the Investigator.

#### 7.5.5 12-Lead Electrocardiogram

The 12-lead ECG recording will be performed at the designated time points as outlined [Appendix 1](#).

Resting 12-lead ECGs will be recorded after the subject has been supine and at rest for at least 5 minutes.

Single 12-lead ECGs will be repeated twice if either of the following criteria apply:

- QT interval corrected for heart rate using Fridericia's method - QTcF interval >500 ms in men and women
- QTcF change from the baseline (pre-dose) is >60 msec.

Additional 12-lead ECGs may be performed at other times if judged to be clinically appropriate or if the ongoing review of the data suggests a more detailed assessment of ECGs is required. The Investigator or designee will perform a clinical assessment of each 12-lead ECG.

Any new clinically significant ECG abnormalities occurring during the study will be recorded as AEs.

#### 7.5.6 Physical Examination

A full physical examination or an abbreviated physical examination will be performed at the timepoints specified in [Appendix 1](#).

A full physical examination includes head/neck/thyroid; eyes/ears/nose/throat (EENT); respiratory; cardiovascular; lymph nodes; abdomen; skin; musculoskeletal; and neurological. Breast, anorectal, and genital examinations will be performed only if medically indicated.

An abbreviated physical examination includes cardiovascular, respiratory, abdominal exams and as indicated based on subject's symptoms.

#### 7.5.7 Safety Data Review

A SRT including 2 physicians from the Sponsor, 1 CRO medical monitor (if needed) and critical cross-functional team members from the Sponsor will meet periodically to review AEs/SAEs, reasons for study discontinuations, and key clinical and laboratory assessments. SRT members will be blinded to subject treatment assignment. The SRT will operate under the SOPs of the sponsor SRT.

The study may be terminated if unexpected, significant, or unacceptable safety risks to enrolled subjects arise, or if recommended by applicable board(s) after review of safety and efficacy data.

## 8 SAMPLE SIZE AND DATA ANALYSES

### 8.1 General Considerations

All statistical analyses will be performed using Statistical Analysis Software (SAS®) Version 9.4 or later. All clinical study data will be presented in subject data listings. Descriptive statistics will be presented for all endpoints and will include number of subjects (n), mean, standard deviation, first quartile (Q1), median, third quartile (Q3), minimum and maximum for continuous variables, and frequency and percentage for categorical and ordinal variables.

Unless otherwise specified, all tests will be two-tailed using pre-specified levels of significance.

Statistical analyses for the Phase 2b portion of the study will be conducted separately. An integrated analysis of the pooled data may be performed at the end of the study depending on the results of these individual analyses. Details for the analyses will be specified in the SAP.

### 8.2 Handling of Dropouts and Missing Data

Criteria for removal of subjects from therapy or assessments are explained in [Section 4.10](#). To the extent possible, attempts will be made to minimize the amount of missing data through measures planned in the study conduct. Details for handling missing values will be specified in the SAP.

### 8.3 Multiple Comparisons/Multiplicity

As this is a dose finding study, there is no multiplicity adjustment planned for the comparisons of multiple doses of KPL-716 versus placebo.

### 8.4 Determination of Sample Size

The Phase 2b sample size calculation is based on the primary efficacy endpoint percentage change from baseline of WI-NRS at Week 16 using a two-sample t-test.

Approximately 180 subjects in total will be equally randomized to the 4 arms of Phase 2b. At Week 16, 53% and 30% reduction in weekly average of WI-NRS are assumed for KPL-716 and placebo arms, respectively. For each comparison, assuming treatment effect of 23% difference in weekly average WI-NRS reduction from baseline at Week 16 and standard deviation of 35%, and two-sided alpha of 0.05, 38 subjects in each arm will guarantee 80% power to the treatment effect. Approximately 45 patients in each arm are required after adjusting for 15% lost follow up.

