**Determination of Sample Size:**

The Phase 2b sample size calculation is based on the primary efficacy endpoint (percentage change from baseline of WI-NRS at Week 16) using a two-sample t-test.

Approximately 180 subjects in total will be equally randomized to the 4 arms of Phase 2b. At Week 16, 53% and 30% reduction in weekly average of WI-NRS are assumed for KPL-716 and placebo arms, respectively. For each comparison, assuming treatment effect of 23% difference in weekly average WI-NRS reduction from baseline at Week 16 and standard deviation of 35%, and two-sided alpha of 0.05, 38 subjects in each arm will guarantee 80% power to the treatment effect. Approximately 45 patients in each arm are required after adjusting for 15% lost follow up.

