The Phase 2a in PN patients, under the regimen of 720 mg loading dose with up to 15 weekly 360 mg SC doses, demonstrated clinical efficacy and an acceptable safety profile. The  $C_{max}$  and  $C_{trough}$  were 235 and 220  $\mu$ g/mL at week 16, respectively, in the 16-week dosing cohort. Clinical efficacy persisted when drug concentration dropped to approximately 30  $\mu$ g/mL among responders 9 weeks after last dosing. However, it is not certain if  $C_{eff}$  is 30  $\mu$ g/mL or lower as the follow-up period may be insufficient. Additionally, the observed exposure metrics from interim PK samples were largely comparable with predicted concentration-time profiles using the updated PK model (including all subjects from KPL-716-C001). This model was thus used to conduct regimen simulation for Phase 2b. Four repeated doses of 540 mg Q4W could reach a steady status with  $C_{trough} \geq 10, 20, \text{ or } 30 \mu\text{g/mL}$  in 95%, 77%, or 51% of subjects, respectively; therefore, this regimen could be efficacious if  $C_{eff}$  is 30  $\mu$ g/mL or lower. Four repeated doses of 360 mg Q4W SC could reach a steady status with  $C_{trough} \geq 5 \mu\text{g/mL}$  in 88% of subjects and  $C_{trough} \geq 10 \mu\text{g/mL}$  in 68% of subjects. This regimen could provide a reasonable coverage for an estimated  $C_{eff}$  of 5-8  $\mu$ g/mL concluded from the cynomolgus monkey itch model study. Four repeated doses of 120 mg Q4W SC could reach a steady status with  $C_{trough}$  above 5 or 10  $\mu$ g/mL in 1.6% or 0.1% of subjects, respectively. Thus, 120 mg Q4W SC is chosen as a subtherapeutic dose. A 16-week treatment/observation is used to allow for at least 4 repeated doses of each regimen to reach steady status. No loading dose is planned to avoid masking onset of efficacy and efficacy differentiation among the different dose regimens. Per the PK simulation, continuous treatment in OLE with 360 mg, SC, Q2W results in at least 96% or 82% of subjects with  $C_{trough} \geq 10 \text{ or } 20 \mu\text{g/mL}$  and  $C_{max}$  and  $C_{trough}$  (i.e., < 100  $\mu$ g/mL) is below the level achieved in the Phase 2a QW dose but higher than the Q4W doses in the blinded portion of the study. It follows that the proposed Q2W OLE dose provides a more robust drug coverage than the Q4W doses while assumed at least as safe as higher Phase 2a QW exposures, thus complementing the exploration for an efficacious and safe dose overall.

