The objective of the Phase 2b study is to define the minimally efficacious dose by exploring the clinical response to varying Ctrough levels. Another objective is to identify a likely practical dosing regimen to carry forward into subsequent confirmatory studies. In the Phase 2b study, subjects will be randomized 1:1:1:1 to receive 4 different dosing regimens of KPL-716 or placebo SC: KPL-716 540 mg SC, Q4W; KPL-716 360 mg SC, Q4W; KPL-716 120 mg SC, Q4W; or placebo SC, Q4W, during the Double-Blind Period. After the Double-Blind Period, all subjects will have the option to receive KPL-716 360 mg SC, Q2W during the OLE Period to evaluate the long-term safety and PK, and to maximize potential benefits but not exceed the doses tested previously (i.e., 720 mg SC or 7.5 mg/kg IV or 360 mg SC weekly).

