1.5. Determination of Sample Size

The Phase 2b sample size calculation is based on the primary efficacy endpoint (percentage change from baseline of WI-NRS at Week 16) using a two-sample t-test.

Approximately 180 subjects in total will be equally randomized to the 4 arms of Phase 2b. At Week 16, 53% and 30% reduction in weekly average of WI-NRS are assumed for KPL-716 and placebo arms, respectively. For each comparison, assuming treatment effect of 23% difference in weekly average WI-NRS reduction from baseline at Week 16 and standard deviation of 35%, and two-sided alpha of 0.05, 38 subjects in each arm will provide 80% power to detect the treatment effect. Approximately 45 subjects in each arm will be randomized assuming 15% drop out during the 16 weeks of treatment.

The sample size calculation was performed using nQuery version 8.5.

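### The 80% power stated for every KPL-716 comparison is not supported for 120 mg, which the protocol chose as a subtherapeutic dose

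*Protocol*

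**What the plan says.** The synopsis of the protocol (Determination of Sample Size) sets the responses: "At Week 16, 53% and 30% reduction in weekly average of WI-NRS are assumed for KPL-716 and placebo arms, respectively". Protocol 8.4 repeats this and applies the resulting difference to every contrast: "For each comparison, assuming treatment effect of 23% difference in weekly average WI-NRS reduction from baseline at Week 16 and standard deviation of 35" per cent, with two-sided alpha 0.05. It concludes that "38 subjects in each arm will guarantee 80% power to the treatment effect", and it raises 38 to about 45 per arm for 15% loss to follow-up, about 180 in total. SAP 1.5 keeps the same inputs with a milder verb: "38 subjects in each arm will provide 80% power to detect the treatment effect".

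SAP section 3 lists the comparisons as 540 mg, 360 mg and 120 mg, each against placebo. SAP 4.6.2 tests a null hypothesis for each dose and reports a 95% confidence interval for each difference.

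Protocol 4.5 describes what the doses are expected to do. For 120 mg the simulated trough exceeds 5 or 10 µg/mL "in 1.6% or 0.1% of subjects, respectively. Thus, 120 mg Q4W SC is chosen as a subtherapeutic dose". For 360 mg the trough is at or above 5 µg/mL in 88% of subjects, and at or above 10 µg/mL "in 68% of subjects. This regimen could provide a reasonable coverage for an estimated" effective concentration of 5–8 µg/mL. For 540 mg the trough is at or above 10 µg/mL in 95%. The section adds: "No loading dose is planned to avoid masking onset of efficacy and efficacy differentiation among the different dose regimens".

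**The concern.** The sample-size sections and the dose rationale describe the 120 mg arm differently. The first gives it the full 23-point effect and 80% power. The second selects it because almost no subject is expected to reach the trough levels considered relevant. A dose chosen on that ground would not be expected to show the same benefit as the other two.

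What is at stake is how a 120 mg result is read. Someone who takes 80% as the power of all three comparisons may treat a non-significant 120 mg result as good evidence that the dose does nothing. With the power that arm may really have, the result would carry little information either way.

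**Working it through.** **Inputs.** From protocol 8.4 and SAP 1.5: difference 23 points (53 − 30), SD 35, two-sided alpha 0.05, two-sample t-test, 38 per arm, 15% dropout, four equal arms. The documents give no effect for 120 mg, so the smaller differences below are assumptions: three quarters, one half and one third of 23.

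**Step 1: reproduce the plan's figure.** Standard error SE = SD × √(2/n). Noncentrality λ = difference / SE. Power = P(|T| > t at 0.975) with 2n − 2 degrees of freedom and noncentrality λ.

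- n = 38: SE = 35 × √(2/38) = 8.03; λ = 23 / 8.03 = 2.86; power 80.7%.
- n = 37: power 79.6%, so 38 is the smallest n that reaches 80%.
- Dropout: 38 / 0.85 = 44.7, rounded up to 45; 4 × 45 = 180.

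All three stated numbers reproduce.

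**Step 2: power when the true difference is smaller.** The range 38 to 45 runs from completers only to all randomized subjects. At n = 45, SE = 35 × √(2/45) = 7.38.

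| True difference (assumed, except 23) | λ, n = 38 | Power, n = 38 | λ, n = 45 | Power, n = 45 |
|---|---|---|---|---|
| 23 (plan) | 2.86 | 80.7% | 3.12 | 86.9% |
| 17.25 (three quarters) | 2.15 | 56.4% | 2.34 | 63.8% |
| 11.5 (half) | 1.43 | 29.3% | 1.56 | 33.8% |
| 7.67 (one third) | 0.96 | 15.6% | 1.04 | 17.7% |
| 0 | 0 | 5.0% | 0 | 5.0% |

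**Step 3: precision of any one comparison.** The half-width of the 95% confidence interval is t × SE.

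- n = 38: 1.99 × 8.03 = 16.0 points.
- n = 45: 1.99 × 7.38 = 14.7 points.

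For example, an observed 120 mg difference of 11.5 points with 38 per arm would have an interval from 11.5 − 16.0 = −4.5 to 11.5 + 16.0 = 27.5. That is not significant, yet it still includes the full 23-point design effect.

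**The case against.** The strongest reply is that the plan contains no mistake. The power sentence is conditional on a 23-point difference, and it is right under that condition. Protocol 4.5 discloses the purpose of 120 mg, a deliberately low anchor arm is normal in dose finding, and SAP 4.6.2 reports an interval for every dose, so the imprecision will be visible. All of this stands, and it keeps the point small. It does not remove the point, because the sentence attaches its condition to every comparison, including the one that protocol 4.5 sets apart. If low power for 120 mg is intended, the sample-size section should say so.

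A reader might infer two stronger points that the documents do not support.

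- **That 360 mg is also underpowered.** Its trough coverage at 10 µg/mL is lower than that of 540 mg (68% against 95%). But protocol 4.5 also gives 88% at or above 5 µg/mL and judges that to be reasonable cover for the estimated effective concentration, which it describes as uncertain. Lower coverage at one threshold does not show a smaller clinical effect.
- **That the dose-finding aim has no analysis.** Protocol 4.5 says: "The objective of the Phase 2b study is to define the minimally efficacious dose by exploring the clinical response to varying" trough levels. The SAP efficacy sections contain only comparisons with placebo. However, this aim is not among the formal objectives, and it concerns exposure rather than nominal dose. SAP 4.9 leaves PK to a separate plan, which is not available here, and protocol 8.8 foresees a possible population PK evaluation outside the study. Whether an exposure-response analysis exists cannot be judged. What can be said is that the SAP does not point to one.

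**Conclusion.** The point holds for 120 mg only, as a matter of wording rather than sample size. The 80% figure is correct for any dose with a true 23-point difference, but it conflicts with the protocol's own expectation for 120 mg. If that dose has between one third and three quarters of the assumed effect, its power is between about 16% and 64%, and its confidence interval extends about 15 to 16 points either side.

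These figures rest on assumed effects for 120 mg, the plan's SD of 35, 38 to 45 subjects per arm and an unadjusted t-test. The planned analysis is a covariate-adjusted ANCOVA with multiple imputation in the mITT set, so actual power could differ somewhat. The conflict between the two sections does not depend on these numbers. The consequence is modest, because the intent for 120 mg is disclosed and intervals are planned. The change is worth considering because it costs almost nothing.

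**What to change.** **Main change, in the protocol synopsis, protocol 8.4 and SAP 1.5.** State three things:

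1. With 38 evaluable subjects per arm, power is 80% for a dose whose true difference from placebo is 23 percentage points, and lower for a smaller difference (about 56% at 17.25 points and 29% at 11.5 points, both illustrative).
2. The 120 mg arm was chosen as subtherapeutic, and 80% power is not claimed for its comparison with placebo.
3. The approximate 95% confidence interval half-width is 16 points (unadjusted, 38 per arm), so a non-significant 120 mg result is not evidence of no effect.

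In the two protocol passages, also replace the verb guarantee with provide, as SAP 1.5 already does.

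**Optional and secondary, in SAP 4.6.2 or 4.9.** If the separate PK plan contains an exposure-response analysis on trough levels that serves the aim in protocol 4.5, cross-reference it. If not, add a supportive one there. The comparisons of each dose with placebo stay primary in either case.

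**Cost.** The stated power becomes less favourable for the low dose. The main change means edited sentences in three places, and the option adds one cross-reference or one supportive analysis. No patients are added, and the primary analysis and the doses stay as planned.
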